Taking into account the above data, it has been hypothesized that inhibition of the IL23/Th17 axis may lead to simultaneous improvement of psoriatic and concomitant atherosclerotic disease (1). To date, isolated studies have shown this association in patients receiving IL17 inhibitors for moderate or severe psoriasis. Specifically, in one study, treatment of patient for one year with an IL17 inhibitor (secukinumab) resulted in improvements in myocardial deformation, arterial elasticity, and coronary artery function, along with significant reductions in psoriasis activity and oxidative stress, findings that were not observed in patients treated with cyclosporine or methotrexate (10). In contrast, another study of patients with psoriasis did not demonstrate a significant benefit in terms of cardiovascular risk in patients treated with IL23/Th17 axis inhibitors (ustekinumab, secukinumab, ixekizumab), which was partly attributed to the short duration of treatment and follow-up (6 months) (11). Finally, in another study, biological therapy with TNF- α , IL17, and IL12/23 inhibitors was associated with reduced coronary inflammation assessed by the perivascular fat attenuation index (12).

Outcomes

The primary outcome is the assessment of the effect of treatment with an IL17 or an IL23 inhibitor on arterial stiffness in patients with moderate-to-severe psoriasis, by evaluating the pulse wave velocity (PWV) and the augmentation index normalized to 75 beats/min (Alx75) at baseline, after 24 and 52 weeks of treatment. Secondary outcomes were the comparison of change in PWV and Alx75 between the study groups and the assessment of change in psoriasis disease severity scores and in ankle-brachial index (ABI)

Patients

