This observational cohort study was performed between September 2021 and September 2024. Consecutive patients with plaque psoriasis with or without psoriatic arthritis, who were monitored in the outpatient department of a tertiary academic hospital for skin diseases were included in the study if they fulfilled all of the following inclusion criteria: 1. Age \geq 18 years; 2. Clinical diagnosis of moderate-to-severe psoriasis (Psoriasis Area Severity Index (PASI) score > 10 or Body Surface Area (BSA) >10 or Dermatology Life Quality Index (DLQI) >10); 3. Treatment with an IL17 inhibitor [secukinumab (Cosentyx[®]), ixekizumab (Taltz[®]), brodalumab (Kyntheum[®])] or an IL23 inhibitor [risankizumab (Skyrizi[®]), guselkumab (Tremfya[®])] or a conventional systemic agent (e.g. methotrexate, cyclosporine) or a small molecule [apremilast (Otezla[®])] as monotherapy for a total of 52 weeks. The exact agent was chosen from the treatment physician of each patient, based on disease characteristics and comorbidities. Patients who did not receive biologic therapy served as a control group. Patients were not included in the if they fulfilled any of the following criteria: 1. Prior therapy with an IL17 or IL23 inhibitor; 2. Prior therapy with an TNFa-inhibitor for up to 3 months before entering the study; 3. Chronic or severe acute infections, malignancy, pregnancy or lactation

Study location

The study will be conducted at the First University Dermatology Clinic of the National and Kapodistrian University of Athens, at the "Andreas Syggros" Hospital of Athens, in

collaboration with the First University Cardiology Clinic of the National and Kapodistrian University of Athens, at the "Hippokratio" Hospital of Athens.

Materials and Methods

The enrollment of patients who will participate in the study will be carried out at the psoriasis clinic of the "Andreas Syggros" Hospital in Athens. All patients will provide written informed consent prior to enrollment in the study. The selection and administration of the biological agent will be done according to the usual practices of the psoriasis clinic based on the characteristics of the patient/disease and the international guidelines for the administration of each drug. Assessment of psoriatic disease and evaluation response will take place before the start of treatment, at week 24 and 52.

Monitoring of psoriasis

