Psoriasis assessment scores including Psoriasis Area Severity Index (PASI), physician global assessment (PGA), Body Surface Area (BSA) and Dermatology Life Quality Index (DLQI) were assessed at baseline, after 24 and 52 weeks of treatment.

Monitoring of cardiovascular parameters

All patients will undergo measurement of carotid-femoral PWV, Alx75 and right and left ABI at baseline, after 24 and 52 weeks of treatment.

Statistical analysis

Statistical analysis will be performed using Statistical Package for the Social Sciences for iOS (version 29.0.2.2 IBM Corp: Armonk, NY, USA). Descriptive statistics will be used to present the patients' characteristics. Variables with normal distribution will be reported as mean \pm standard deviation (SD), while not normally distributed outcomes will be reported as median values and range. Categorical variables will be presented as frequencies and percentages. Between-group analysis will be performed using the Kruskal-Wallis Test and Student's t-test or one-way ANOVA test. Statistical significance is determined at a two-tailed p value of 5% (0.05).

Funding

The biological agents that will be administered are approved for the treatment of moderate/severe psoriasis in Greece, so the cost of treatment will be covered by each patient's insurance after electronic prescription of each drug. The laboratory test that will be performed is part of the usual practice of monitoring treatment with biological agents, so the costs will be covered by the patient's insurance, after electronic prescription. There will be no external funding for the study.

Principal investigator

[name]

Subinvestigators

[name]

[name]

[name]

[name]

[name]

[name]

[name]

[name]

[name]

[name]

[name]

References

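### PWV and AIx75 are read at three visits, but the plan names only one-value-per-patient tests and no missing-reading rule; week-24 and week-52 results can rest on different patients, and week 52 may be biased

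*Combined protocol and SAP*

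**What the plan says.** The section Monitoring of cardiovascular parameters schedules, for every patient, PWV, AIx75 and "right and left ABI at baseline, after 24 and 52 weeks of treatment". Under Outcomes, the primary outcome is the effect of an IL17 or IL23 inhibitor on PWV and AIx75 over those three time points; comparing the change between study groups is secondary.

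The only inferential methods are in one sentence under Statistical analysis: "Between-group analysis will be performed using the Kruskal-Wallis Test and Student's t-test or one-way ANOVA test". The section adds a two-sided 0.05 level. Nowhere do the documents give a repeated-measures or mixed model, an analysis set, a rule for missing readings, an imputation method or a sensitivity analysis. They also do not say how the three visits enter the named tests.

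Under Patients, one inclusion criterion is treatment "as monotherapy for a total of 52 weeks". That limits who is in the cohort. It does not require a complete set of vascular readings.

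**The concern.** Each named test takes one number per patient per comparison, whether a reading or a change. With no missing-reading rule, a patient who has baseline and week-24 values but no week-52 value contributes nothing at week 52, although the week-24 value carries information about the missing one.

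Two things are at stake. First, a difference between the week-24 and week-52 results could reflect who was measured rather than time on treatment. That contrast matters here: the Background section reports a study without significant cardiovascular benefit and attributes this partly to only 6 months of treatment and follow-up. Second, if patients whose vessels are not improving are more often absent at week 52, the mean change among those measured looks better than it is.

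**Working it through.** The plan states no sample size, SD, effect size or dropout rate, so there is no figure of its own to reproduce. **Every input below is an assumption.**

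**1. How far the two visit sets can differ.** Suppose each follow-up reading is missed independently with probability d. Among patients with at least one follow-up reading, the share who are in only one of the two sets is 2d(1-d)/(1-d²) = 2d/(1+d).

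- d = 5%: 0.10/1.05 = 9.5%
- d = 10%: 0.20/1.10 = 18%
- d = 20%: 0.40/1.20 = 33%

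**2. Within-group bias at week 52, by simulation.** Inputs: n = 40, PWV SD 1.5 m/s, between-visit correlation 0.7-0.8, true week-52 change -0.50 m/s, log-odds of a missing week-52 reading rising by 0.7-1.0 per SD of worse week-24 PWV change.

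| Missing at week 52 | Overstatement of change (m/s) | As share of 0.50 |
|---|---|---|
| 5% | 0.02-0.03 | 4-6% |
| 10% | 0.03-0.06 | 6-12% |
| 25% | 0.08-0.12 | 16-24% |

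If missingness is random there is no bias, and using all visits reduces the standard error by only about 3% (at 25% missing).

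For scale, the SD of change is 1.5 × √[2(1-ρ)], which is 1.16 at ρ = 0.7 and 0.95 at ρ = 0.8. With 40 patients the standard error is 1.16/√40 = 0.18 or 0.95/√40 = 0.15. With 30 measured (25% missing) it is 1.16/√30 = 0.21 or 0.95/√30 = 0.17. The bias is below one standard error throughout the table.

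**3. Between-group bias, in closed form.** Let r be the share of good responders, g the gap in mean vascular change between good and poor responders (SD units), and m0 and m1 the probabilities that a good or a poor responder misses week 52. The share of good responders among those measured is r' = r(1-m0)/[r(1-m0) + (1-r)(1-m1)], and the within-group bias is g(r' - r). The between-group bias is the difference of the two within-group values.

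Take m0 = 5%, m1 = 50%, g = 1.0:

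- r = 0.8: r' = 0.76/(0.76 + 0.10) = 0.884, bias 0.084 SD
- r = 0.5: r' = 0.475/(0.475 + 0.25) = 0.655, bias 0.155 SD
- Between groups: 0.084 - 0.155 = -0.071 SD, towards no difference

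Across m1 = 20-50%, the between-group bias runs from -0.017 to -0.071 SD at g = 1.0 and from -0.004 to -0.018 SD at g = 0.25. It is zero when g = 0, or when response and missingness are the same in both groups.

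**4. How much a model of the vascular readings repairs.** If absence depends on the observed week-24 PWV change, as in step 2, an all-visits likelihood analysis returns -0.50 m/s. That follows from the set-up, since the model conditions on the variable that drives absence. If absence instead follows a skin response correlated 0.2-0.5 with week-52 vascular change, the all-visits model removes only about 20-40% of the bias. A separate two-group simulation agrees. It assumed 100 per group, good responders 80% against 50%, and week 52 missed by 40% of poor and 5% of good responders. The true difference was 0.30, the available-case estimate 0.25 and the all-visits estimate 0.27, so (0.27 - 0.25)/(0.30 - 0.25) = 40% of the bias was removed.

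**The case against.** The strongest reply is that the problem may be small. Readings are scheduled for all patients. As written, the 52-week monotherapy criterion already puts patients who stop or switch outside the cohort at both follow-up visits. What remains is patients who stay on treatment but miss a reading, and nothing in the documents suggests that this would be as many as 25%. At 5-10% the bias in step 2 is well inside the standard error. This stands, and it is why the size is given as a range from 5% upwards.

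A second reply is that the named tests are between-group, whereas step 2 concerns change within one group, for which no test is named. This also stands: a reader might infer that the planned comparisons are overstated by up to about a quarter, but that percentage belongs to the within-group change at 25% missing. In the between-group cases of step 3 the bias is small and towards no difference. It could approach the within-group size if absence related to response were confined to one group.

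Two further inferences are tempting and unsupported. One is that a mixed model would fully restore the true value; step 4 shows that this depends on what drives absence. A patient may well react to the skin, and the Background section only hypothesises that skin and vascular responses move together. The other is that the arrangement described as "collaboration with the First University Cardiology Clinic of the National and Kapodistrian University of Athens" makes missed readings likely. The documents do not say where the readings are taken, or that working across two hospitals causes absences.

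None of this removes the gap: a three-visit primary outcome has no longitudinal analysis and no missing-reading rule.

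**Conclusion.** The point holds in conditional form. As written, a missing reading removes the patient from that comparison, the week-24 and week-52 sets can differ, and the week-52 change may be biased if absence is related to response. The documents do not support saying that week 52 is biased: they report no missingness, and that poor responders stay away is plausible but undocumented.

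On the stated assumptions the within-group overstatement is a few hundredths of a m/s at 5-10% missing and about a tenth at 25%. It is zero under random missingness. The actual size is unknown. This is a worthwhile and cheap improvement to the analysis, and it does not show that the study's conclusions would be wrong.

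**What to change.** In the Statistical analysis section:

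- Analyse PWV and AIx75 each with one linear mixed model for repeated measures on all available readings, with group, visit and group-by-visit terms and an unstructured covariance. Read the week-24 and week-52 changes, and the group differences, from that model.
- Use the skin scores already collected at the same time points (for example PASI) as auxiliary variables: impute missing vascular readings from the vascular and skin data within group, fit the same model to each imputed data set, and combine the results. Where the week-52 skin score is missing too, the week-24 score still contributes.
- Define the analysis set, and say whether the 52-week criterion is applied at entry or afterwards.
- Tabulate the number of readings by group and visit, and show the complete-case result as a sensitivity analysis.

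The cost is a rewritten paragraph and somewhat more analysis work, with no new data. The analysis relies on missing-at-random given the vascular and skin data, which is weaker than what the complete-case tests need but still cannot be verified. It does not repair selection from the 52-week monotherapy criterion, which acts on who is in the cohort at both follow-up visits.

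### Student's t-test and one-way ANOVA pool one variance across groups whose size and make-up are not controlled, so the 5% error rate is not protected; Welch versions would protect it for roughly normal changes

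*Combined protocol and SAP*

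**What the plan says.** The Statistical analysis section of the combined protocol and SAP has one sentence on comparing groups: "Between-group analysis will be performed using the Kruskal-Wallis Test and Student's t-test or one-way ANOVA test". The significance level is two-tailed 0.05. The section gives no unequal-variance version of the "t-test or one-way ANOVA test", no check of equal variances, and no rule for choosing among the three tests. Normality is mentioned only for descriptive reporting.

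The Outcomes section makes the group comparison of change a secondary outcome: "Secondary outcomes were the comparison of change in PWV and Alx75 between the study groups". No other between-group method appears, so it is a fair inference, though not written out, that these tests are meant for it.

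The Patients section describes how the groups arise. Enrolment is consecutive, with no target size or ratio. On the choice of drug it says: "The exact agent was chosen from the treatment physician of each patient, based on disease characteristics and comorbidities". The comparator is defined by exclusion: "Patients who did not receive biologic therapy served as a control group". It takes in those on monotherapy with "or a conventional systemic agent (e.g. methotrexate, cyclosporine) or a small molecule". The IL17 group may contain three named agents and the IL23 group two.

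**The concern.** Student's t-test and classical one-way ANOVA estimate a single variance from all groups together. Their stated error rate is exact if the variances are equal and approximately right if the group sizes are equal. When both differ, the pooled standard error is wrong. It is too small if the smaller group is the more variable one, and too large if the larger group is.

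Nothing in the design secures either condition. Sizes follow from who attends and what the physician prescribes. Patients are steered to groups by disease characteristics and comorbidities, which makes unequal spread of change plausible. At stake are the p values and intervals for change in PWV and AIx75 between groups: a difference could be declared too readily, or a real one missed, because of an assumption that the plan need not make.

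**Working it through.** **Inputs from the documents.** Two-tailed alpha 0.05; Student's t, one-way ANOVA and Kruskal-Wallis (Statistical analysis); groups formed by physician choice, no sizes set (Patients). The documents give no group sizes, SDs of change, sample size or power.

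**Assumed inputs.** Group sizes and SD ratios, varied below; normal data; no true difference.

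**Step 1: the plan's own figure.** With equal SDs, simulation (100,000 data sets per scenario) gives a size of 4.95% to 5.05% for Student's t at 30/30, 40/20, 45/15 and 80/20, and 5.00% to 5.09% for ANOVA over five three-group splits. The 5% is reproduced under the tests' own assumption, at any split tried.

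**Step 2: why 30 v 15 drifts.** Let the larger group (n = 30) have SD 1 and the smaller (n = 15) SD r.

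- True variance of the difference: V = 1/30 + r²/15
- What the pooled formula estimates on average: P = [(29 + 14r²)/43] × (1/30 + 1/15) = [(29 + 14r²)/43] × 0.1
- The critical value of t on 43 df is 2.017, but the test behaves as if it were 2.017 × √(P/V). Reading that off the t distribution on 43 df gives an approximate size.

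| r | V | P | √(P/V) | Effective critical value | Approximate size |
|---|---|---|---|---|---|
| 1 | 0.1000 | 0.1000 | 1.000 | 2.017 | 5.0% |
| 1.25 | 0.1375 | 0.1183 | 0.928 | 1.871 | 6.8% |
| 1.5 | 0.1833 | 0.1407 | 0.876 | 1.767 | 8.4% |
| 2 | 0.3000 | 0.1977 | 0.812 | 1.637 | 10.9% |

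Simulation agrees: about 7%, 8.5% and 11% for r = 1.25, 1.5 and 2.

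**Step 3: three groups.** ANOVA at 30/30/15, with the group of 15 more variable by 1.25, 1.5 or 2: about 7%, 8.5% and 12%.

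**Step 4: the other direction.** If the larger group is 1.5 or 2 times as variable, Student's t at 40/20 has size 2.7% and 1.7%. ANOVA at 40/40/15, with the two larger groups more variable, has 3.3% and 2.9%.

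**Step 5: where the pooled tests hold.** At 30/30, Student's t stays between 4.9% and 5.2% even at an SD ratio of 2. At 20/20/20, ANOVA with unequal SDs runs from 5.3% to 6.1%.

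**Step 6: Welch versions.** Over all the assumed normal scenarios in the 100,000-replicate runs, the size is 4.9% to 5.3%.

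**Step 7: what Welch costs if variances are equal** (power, pooled v Welch).

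| Split | Pooled | Welch | Loss (points) |
|---|---|---|---|
| 30/30 | 78.8% | 78.8% | 0.0 |
| 40/20 | 78.4% | 77.7% | 0.7 |
| 45/15 | 78.6% | 76.6% | 2.0 |
| 80/20 | 79.1% | 77.3% | 1.8 |
| 20/20/20 | 77.6% | 76.3% | 1.3 |
| 40/40/15 | 78.2% | 75.9% | 2.3 |
| 30/20/10 | 77.7% | 73.8% | 3.9 |
| 40/15/10 | 77.8% | 72.7% | 5.1 |
| 90/10 | 79.0% | 72.3% | 6.7 |
| 40/40/5 | 78.1% | 66.6% | 11.5 |
| 50/5 | 78.5% | 61.2% | 17.3 |

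**The case against.** The strongest objection is that no failure has been shown. A reader might infer that the 5% level does not hold in this study. The documents do not support that: sizes that are not controlled need not be unequal, mixed make-up need not mean unequal variance, and both must occur together for material harm. This stands, and the point is limited to a risk.

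A reader might also infer that the non-biologic group must be the more variable one because it mixes drugs. Every group may mix drugs, and nothing in the documents gives the direction. The error could equally be conservative.

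Larger figures can be produced by merging IL17 and IL23 patients against the rest. At 60 v 15, Student's t has a size of about 12% and 18% at SD ratios of 1.5 and 2. The plan never states that contrast, so those figures should not carry the point. A ratio of 2 is in any case a fourfold difference in variance.

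It is tempting to say that Welch is free and always correct. Neither is so. The loss is real when a group is very small, which uncontrolled sizes cannot rule out. With strongly skewed changes at 60 v 15, Welch's size is about 6.7% to 8.4%. The plan expects that some outcomes may not be normal, so Kruskal-Wallis should stay. It does not remove the concern, though. The plan does not say when it applies, and its own size at 30/30/15 is about 5.6%, 6.4% and 7.9% when the smaller group is 1.25, 1.5 or 2 times as variable.

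Finally, the comparison is secondary and open to confounding by physician choice, which Welch leaves untouched. That limits the weight of the point, but is no reason to keep an avoidable assumption.

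**Conclusion.** The point holds as a conditional one. The plan names pooled-variance tests, with no unequal-variance version, for groups whose sizes and make-up the design leaves open. The 5% level is therefore unprotected. In the 30 v 15 and 30/30/15 settings, the true size is about 7% for mild inequality of spread and 11% to 12% for a doubled SD in the smaller group. It falls to about 2% to 3% in the reverse cases shown. Welch versions hold about 5% throughout for normal data. These sizes rest on assumed group sizes, assumed SD ratios and normal changes, and on the inference that the named tests will be applied to change. A Welch analysis would not by itself make a difference between groups attributable to treatment. The point is a cheap improvement to a secondary analysis.

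**What to change.** In the Statistical analysis section, replace Student's t-test and one-way ANOVA by Welch's t-test (two groups) and Welch's ANOVA (three groups) with Games-Howell pairwise intervals, for between-group comparisons of change that are approximately normal. Keep Kruskal-Wallis for clearly non-normal changes, and state that this is its role. Say explicitly that these methods apply to change in PWV and AIx75. Fixing the choice in advance also prevents choosing between pooled and Welch results after the data are seen.

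The cost is a sentence or two of text and no new data. If variances are in fact equal, expect to lose about 0 to 2 points of power for two groups up to 4:1 and about 1 to 5 points for moderate three-group splits. The loss is about 7 to 17 points in extreme splits where one group has only 5 to 10 patients (90/10, 40/40/5, 50/5). Confounding by choice of agent needs its own remedy.
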